1.2. Study Objectives and Endpoints

The aim of this study is to evaluate safety, tolerability, and efficacy of PRCL-02 in patients with moderate to severe chronic plaque psoriasis. There will be three parallel treatment arms: 2 dose levels of PRCL-02 and a placebo arm. Patients will be randomized in 1:1:1 ratio to PRCL-02 Dose 1:PRCL-02 Dose 2:Placebo.

Table 1 shows the objectives and endpoints of the study.

Table 1. Objectives and Endpoints

Objectives	Endpoints
Primary	
To evaluate the efficacy of PRCL-02 after 12 weeks of once daily oral dosing in patients with moderate to severe chronic plaque psoriasis	A 75% improvement from baseline to Week 12 in the PASI (PASI 75)
Secondary	
To evaluate the safety and tolerability of PRCL-02 after 12 weeks of once daily oral dosing in patients with moderate to severe chronic plaque psoriasis	Treatment emergent adverse events
To characterize the pharmacokinetics (PK) of PRCL-02 after multiple once daily oral dosing for 12 weeks, in patients with moderate to severe chronic plaque psoriasis	AUC _{0-τ} , C _{max} , t _{max} at steady state
Exploratory	
To evaluate clinical response to PRCL-02 over time using the PASI and sPGA	
 • PASI • sPGA
To explore the PK/PD exposure-response relationships of PRCL-02	The relationship between PRCL-02 exposure and selected PD efficacy and/or safety measures

1.3. Sample Size Determination

Approximately 27 patients will be randomized to each of the 3 treatment arms for a total of 81 patients. The sample size was chosen so that there is at least 80% power to detect an increase in response of 30% or more for the primary objective (percentage of patients reaching a PASI 75 at week 12) in any PRCL-02 treatment arm relative to placebo using a one-sided Fisher's Exact test with a 10% type 1 error rate. This assumes a placebo response of 7.5% and PRCL-02 response of 37.5% in either PRCL-02 treatment arm for the primary end point, based on available clinical data from marketed injectable and oral targeted therapies for psoriasis. The sample size was calculated assuming a 10% drop out of patients in each arm and that drop-outs would be analyzed as non-responders.

2. GENERAL STATISTICAL METHODOLOGY AND CONVENTIONS

2.1. General Considerations

All computations for statistical analyses will be performed using SAS® software, Version 9.4 or later. All SAS programs used in the production of statistical summary outputs will be validated with independent programming prior to finalization. In addition, all program outputs will be independently reviewed. The validation process will be used to confirm that all data manipulations and calculations were accurately done. Once validation is complete, a senior statistical reviewer will perform a final review of the documents to ensure the accuracy and consistency with this plan and consistency within tables. Upon

completion of validation and quality review procedures, all documentation will be collected and filed by the project statistician or designee.

Before implementation of parametric methods of analysis, the distribution of analysis variables will be examined to determine if model assumptions are satisfied. Transformations or nonparametric methods of analysis may be used if warranted. However, in some cases, nonparametric analysis may be the initially proposed method due to the expected distribution of response. Whenever alternative methods of analysis are required, the description of the new method along with the rationale for its use will be documented in the CSR.

The eCRF data for all patients will be provided in Standard Data Tabulation Model (SDTM) datasets. Data listings supplied as part of the CSR will be sorted by investigative site and patient identification number, and patients will be identified in the listings by the investigator number concatenated with the patient number.

2.2. Randomization and Unblinding Plan

This is a double-blind study; both patients and investigators will be blinded. Eligible patients will be 1:1:1 randomized to one of 3 arms (2 treatment and 1 placebo) within 28 days following screening. Assignment to treatment groups will be determined by a computer-generated random sequence using an interactive web-response system (IWRS). The IWRS will be used to assign blister packs containing double-blind drug product to each patient. The IWRS system will be programmed using an adaptive allocation scheme to balance the treatment arms according to the following baseline measurements:

- weight (< 95kg and \geq 95kg), and
- prior number of failed therapies (< 3 and \geq 3).

To preserve the blinding of the study, no study personnel will see the randomization table and treatment assignments before database lock.

Emergency unblinding for AEs may be performed through the IWRS, or other means if necessary. Emergency unblinding may be used ONLY if the patient's well-being requires knowledge of the patient's treatment assignment.

Unblinding will occur after the last patient completes the study and all data management activities have been completed (i.e. data entered, coding completed, and all queries resolved).

2.3. Analysis Populations

The analysis populations are described in Table 2.

Table 2. Analysis Populations

Population	Description
Randomized	All patients who sign informed consent and were randomized.
Safety	All randomized patients who take at least 1 dose of double-blind study treatment. In the event of a treatment error, patients will be analyzed according to the treatment they actually received.

Population	Description
Intent-to-Treat (ITT)	All randomized patients with moderate to severe chronic plaque psoriasis who take at least 1 dose of double blind study treatment and have at least the Week 1 post-baseline PASI assessment. In the event of a treatment error, patients will be analyzed according to the treatment to which they were randomized.
Pharmacokinetic	All randomized patients who take at least 1 dose of double blind study treatment and provide sufficient data for pharmacokinetic assessments.

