Safety: Safety analyses will be conducted on the Safety analysis set. Safety parameters that will be assessed include: adverse events, clinical laboratory parameters, vital signs, electrocardiogram parameters, and physical examination. The parameters will be listed and summarized using standard descriptive statistics.

Pharmacokinetics/Pharmacodynamics: Plasma PRCL-02 PK parameters after multiple dose administration will be calculated using noncompartmental methods. Pharmacokinetic parameters

will be summarized by dose level using descriptive statistics. Mean and individual PRCL-02 plasma concentration-time curves will be represented graphically.

The PK/PD relationship between PRCL-02 exposure and PD efficacy and/or safety measures may be explored.

2. Schedule of Activities

Table PRCL 1 **Schedule of Activities**

Procedure	Screening ^a	1	2	3	4	5	6	7	8	9	FU	EoS ^b
Visit #												
Study Days	-28 to -1	1	8	15	29	57	85	99	113	127		141
Window Period (Days)		±2	±2	±2	±2	±2	±2	±2	±2	±2		±2
Week	-	-	1	2	4	8	12	14	16	18		20
Informed consent	X											
Demographics	X											
Medical history	X											
Inclusion and exclusion criteria	X	X										
Pregnancy test (♀) ^c	X	X	X	X	X	X	X	X	X	X		
Serum FSH (PMP ♀)	X											
QuantiFERON TB Test ^d	X											
HIV/hepatitis screen	X											
Randomization		X										
Study drug dispensing ^e		X	X	X	X	X						
Study drug accountability			X	X	X	X	X					X if ET
Safety Evaluations												
Physical examination ^f	X	X	X	X	X	X	X					X
Height/weight ^g	X	X	X	X	X	X	X					X
Vital signs (pulse and BP) ^h	X	X	X	X	X	X	X	X	X	X		X
12-lead ECG ⁱ	X	X	X	X	X	X	X					X
Clinical laboratory tests ^j	X	X	X	X	X	X	X					X
AE monitoring	X	X	X	X	X	X	X	X	X	X		X
Concomitant medications	X	X	X	X	X	X	X	X	X	X		X
Efficacy and Other Evaluations												
PASI	X	X	X	X	X	X	X	X	X	X		X
sPGA	X	X	X	X	X	X	X	X	X	X		X
PK sampling ^k			X	X	X	X	X	X	X	X		X
Plasma sample collection for PGx assessments		X										

Abbreviations: AE = adverse event; BP = blood pressure; ECG = electrocardiogram; EoS = end-of-study; FSH = follicle stimulating hormone; FU = Follow-up; HIV = human immunodeficiency virus; PGx = pharmacogenomics; PK = pharmacokinetics; PMP = postmenopausal; S = screening; sPGA = static physician's global assessment; TB = tuberculosis.

- ^a Randomization will be within 28 days following the screening visit.
- ^b In the event of early or premature discontinuation, a patient should undergo all activities per the EoS visit.

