10.2. Populations for Analyses

For purposes of analysis, the following populations are defined:

Population	Description
Randomized	All patients who signed informed consent and are randomized.
Safety	All randomized patients who take at least 1 dose of double-blind study treatment. In the event of treatment error, patients will be analyzed according to the treatment they actually received.
Intent-to-Treat (ITT)	All randomized patients with moderate to severe chronic plaque psoriasis who take at least 1 dose of double-blind study treatment and at least the Week 1 post-baseline PASI assessment. In the event of a treatment error, patients will be analyzed according to the treatment to which were randomized.
Pharmacokinetic	All randomized patients who take at least 1 dose of double-blind study treatment and provide sufficient data for pharmacokinetic assessments.

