2.6. Definition of Study Visit

Patient data will be analyzed according to the nominal visit collected in the eCRF. Unscheduled visits at which safety data is collected (e.g. labs and ECGs) may result in clinically significant findings or withdrawal, which will be included in adverse event and/or disposition summaries.

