2.7. Handling of Dropouts and Missing Data

Dates

Imputation of missing or partial dates is not expected, but if a complete date is required for calculations, the following algorithms will be applied:

- For the start date:
 - If year, month, and day are missing then use the minimum of the patient's first visit date or the consent date.
 - If either only month or month and day are missing then use January 1.
 - If only day is missing, impute the first day of the month.

- For the end date:
 - If year, month, and day are missing then use the patient's last visit date.
 - If either only month or month and day are missing then use December 31.
 - If only day is missing then use the last day of the month.
 - Do not expand the record past the patient's last visit.

The original missing or partial date, the imputed complete date, and the indicator variable that indicates which dates were imputed will be retained in the database.

PASI and sPGA Response

Patients whose response to treatment cannot be determined due to missing data (including early withdrawal) will be considered non-responders in the analyses.

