5. EFFICACY ANALYSES

5.1. Primary Analysis

Efficacy endpoints will be assessed using the ITT population.

The primary treatment effect will be measured as the difference between each active treatment arm and placebo in the percentage of patients with a $\geq 75\%$ improvement from baseline in PASI (PASI 75) at 12 weeks.

A one-sided Fisher's exact test with a 10% type 1 error rate will be used to compare each PRCL-02 treatment arm to placebo. Point estimates for the treatment differences (PRCL minus placebo) will be calculated using a lower 90% exact unconditional confidence interval.

Supporting Analysis of the Primary Endpoint

The primary treatment difference may be analyzed using only those patients with a Week 12 PASI assessment; that is, no imputation made for early withdrawal.

The primary treatment differences may be analyzed using a Cochran-Mantel-Haenszel test, adjusting for the four strata used in the randomization [weight (< 95kg and $\geq 95\text{kg}$), and prior number of failed therapies (< 3 and ≥ 3)] if there are a sufficient number of patients in each cell.

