5.3. Exploratory Analyses

The percentage of patients with a $\geq 90\%$ improvement from baseline in PASI (PASI 90) at 12 weeks will be analyzed similarly to PASI 75. PASI 75 and PASI 90 will be summarized at each scheduled visit.

Observed values of the PASI score and subscores, the sPGA score, and the change and percent change from baseline to each scheduled visit will be summarized using descriptive statistics and the treatment groups compared using analysis of variance methods.

The quantitative secondary efficacy endpoints will be assessed by analyzing the change from baseline to the 12-week time point using PROC MIXED to model the difference in the Week 12 change from baseline score between treatment groups and to handle missing assessments. The change from baseline to each scheduled post-baseline visit will be estimated using repeated measures mixed models assuming data are missing at random, with covariates for baseline and visit. The lower 95% confidence limit of the difference in mean scores at Week 12 (PRCL minus Placebo) will be estimated from the mixed model. The effects of baseline scores and treatment will be allowed to vary across visits. The following example SAS code will be used, for assessments at Weeks 1, 2, 4, 8, and 12. For patients who withdraw prior to Week 12, data from the early termination visit will be used as the next visit's assessment; for example, if a patient's last scheduled assessment is at Week 4, the early termination data will be included in the analysis as Week 8.

```
proc mixed;
  class visit treatment patient;
  model endpoint=week*baseline week*treatment;
  repeated week / type=vc subject=patient;
  random patient;
run;
```

In addition, plots of each least squares mean (\pm standard error) for the scores by scheduled visit will be created

If the data appear non-Normal or if a reasonable variance-covariance structure cannot be fit to the data, the treatment comparisons will be made using Wilcoxon Rank-Sum tests at each visit using the observed data.

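### The primary ITT set requires a Week 1 PASI, so dosed patients without one drop out of the denominator instead of counting as non-responders

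*SAP*

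**What the plan says.** SAP 2.3 (Table 2) defines the ITT set as randomised patients with moderate to severe plaque psoriasis "who take at least 1 dose of double blind study treatment and have at least the Week 1 post-baseline PASI assessment". Protocol 10.2 carries the same condition: "take at least 1 dose of double-blind study treatment and at least the Week 1 post-baseline PASI assessment". SAP 5.1 runs the primary analysis on this set: a one-sided Fisher's exact test at 10%, each active arm against placebo, on PASI 75 at Week 12.

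On drop-outs, SAP 2.7 says "Patients whose response to treatment cannot be determined due to missing data (including early withdrawal) will be considered non-responders in the analyses". SAP 1.3 says "The sample size was calculated assuming a 10% drop out of patients in each arm and that drop-outs would be analyzed as non-responders". Neither makes an exception for the first week.

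Three further places bear on who has a Week 1 PASI and what happens to those who do not:

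- Protocol Section 2, footnote b: "In the event of early or premature discontinuation, a patient should undergo all activities per the EoS visit". Those activities include a PASI.
- SAP 2.6: "Patient data will be analyzed according to the nominal visit collected in the eCRF". SAP 5.3 adds, for the mixed model only, that "For patients who withdraw prior to Week 12, data from the early termination visit will be used" as the next visit's assessment.
- SAP 5.1, supporting analysis: "The primary treatment difference may be analyzed using only those patients with a Week 12 PASI assessment".

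**The concern.** Membership of the primary set depends on something that happens after dosing. The set is fixed before the missing-data rule is applied, so a dosed patient who leaves in the first week without a qualifying PASI never reaches the non-responder rule in SAP 2.7. Patients who leave after Week 1 are not affected. The plan thus handles drop-outs in two ways, depending on when they leave.

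Two points of wording make the set uncertain:

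- Taken literally, the condition asks for the Week 1 assessment itself. A patient who missed only that visit would be dropped despite an observed Week 12 PASI.
- An early leaver may have an early-termination PASI, but nothing outside the mixed model says whether it can stand in for Week 1. Two programmers could build different primary sets.

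If first-week loss or missed Week 1 visits differ between arms, the comparison loses the protection of randomisation, and the bias can favour either side. The only missing-data supporting analysis in SAP 5.1 is optional and narrows the set further.

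**Working it through.** **Inputs.** From SAP 1.3 and 5.1: 27 per arm; response 7.5% on placebo and 37.5% on active; 10% drop-out counted as non-response; one-sided Fisher's exact test at 0.10. Assumed: k first-week leavers per arm, k = 0 to 3. For scale, 10% of 27 is 2.7 drop-outs per arm over the whole study. A 25% active response is also assumed, to show a case nearer the decision boundary.

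**The plan's own figure.** With drop-outs as non-responders, the rates become 0.9 × 37.5% = 33.75% and 0.9 × 7.5% = 6.75%. Enumerating all outcomes of two binomials with n = 27 and rejecting when p ≤ 0.10 gives 84.2% power. With 24 completers per arm at the undiluted rates, power is 85.3%. The claim of at least 80% is reproduced either way.

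**Shift in the estimate.** Let r be the response rate among those who stay. Counting k leavers gives r × (27 − k)/27; excluding them gives r. The difference is r × k/27. At r = 37.5% this is 1.4, 2.8 and 4.2 percentage points for k = 1, 2 and 3.

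**Single-patient changes in the decision.** The one-sided p is the upper hypergeometric tail (active against placebo).

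| Situation | All 27 kept | One patient removed |
|---|---|---|
| Active non-responder removed | 9/27 vs 4/27, p = 0.101 | 9/26 vs 4/27, p = 0.087 |
| Placebo non-responder removed | 5/27 vs 1/27, p = 0.096 | 5/27 vs 1/26, p = 0.104 |
| Active Week 12 responder removed for a missed Week 1 (literal reading) | 7/27 vs 2/27, p = 0.071 | 6/26 vs 2/27, p = 0.113 |

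**Chance of a significant result.** Exact enumeration, with k leavers either counted as non-responders in 27 or removed. Response among stayers is 25% on active and 7.5% on placebo.

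| k | Active arm only: counted / excluded | Placebo only: counted / excluded | Both arms: counted / excluded |
|---|---|---|---|
| 1 | 53.6% / 54.6% | 58.2% / 54.3% | 55.1% / 55.8% |
| 2 | 50.3% / 51.2% | 59.7% / 53.2% | 53.3% / 53.9% |
| 3 | 47.0% / 53.8% | 61.2% / 54.6% | 51.5% / 52.0% |

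At the design rates (37.5% against 7.5%), three active-only leavers give 80.9% counted and 85.4% excluded.

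**No true difference (7.5% in both arms), active-only leavers.** Counted and excluded agree at 2.7% for k = 1 and 2.4% for k = 2. At k = 3 they are 2.1% and 4.3%, still below 10%. The jump at k = 3 comes from the discreteness of Fisher's test.

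**The case against.** The strongest reply is that the problem is small and may rarely arise. For one or two active-only leavers at 25% against 7.5%, the chance of significance moves by only about 1 point. Three leavers in one arm would put the whole planned 10% drop-out into the first week of that arm, and nothing in the documents supports that. This stands as a limit on size. It does not remove the single-patient changes, and a single placebo-only leaver already moves the chance by about 4 points, against the drug.

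Secondly, stopping treatment need not mean losing the Week 1 PASI. Protocol Section 8 asks patients who discontinue to complete follow-up procedures, and early leavers should have a PASI at termination. This also stands in part: only those without a qualifying PASI are clearly excluded. But whether a termination PASI qualifies is not stated.

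Thirdly, the Week 1 condition may have been meant as any one post-baseline PASI, and SAP 2.7 may be read as acting only within the defined set. The first reading would spare patients who missed only Week 1, but it needs a wording change and would still exclude early leavers with no PASI. The second removes the formal contradiction with SAP 2.7, but leaves the set at odds with the sample-size assumption.

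Finally, SAP 4.1 tabulates the analysis sets by arm, so an imbalance would be visible, and Protocol 10.3.1 allows optional supportive analyses of early withdrawal. Neither commits to an analysis that includes these patients. Protocol 8.2 lets the sponsor replace discontinued patients, so the exact denominators shown may not arise, but a replacement does not put the excluded patient back.

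**Conclusion.** The concern holds and should be fixed. Both documents make the primary set depend on a post-dose assessment, and this departs from the plan's own rule that drop-outs count as non-responders. Under the assumed 0 to 3 early leavers per arm, the active-arm estimate rises by about 1.4 points per excluded active leaver at 37.5% response, and a borderline decision can change in either direction. The power claim stands, and in the null cases computed the rejection rate stays below 10%. Early loss that is equal in both arms has little effect: the counted and excluded figures differ by less than 1 point at 25% against 7.5%. Loss that differs between arms is a possibility and not a forecast, since the documents give no early-loss rate by arm.

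**What to change.** In SAP Table 2, delete the clause that requires the Week 1 PASI, and make the same change in Protocol 10.2. The primary set is then all randomised, dosed patients, with the disease wording unchanged, analysed as randomised; anyone without a Week 12 PASI is a non-responder under SAP 2.7. Randomised patients who were never dosed stay outside the set, as now. Keep the present set as a sensitivity analysis, and state there whether an early-termination PASI before Week 1 meets the Week 1 condition. Make the change before database lock and unblinding.

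The cost is wording only: no new data and no larger sample. SAP 1.1 gives the SAP precedence over the protocol's statistical sections, so the SAP edit would govern the analysis. Under Protocol 10.3.1, a protocol amendment is needed only if the primary analysis set is judged a principal feature; otherwise the change and its reason go in the clinical study report. Observed response rates may be slightly lower.

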2.4. Treatment Groups

This study involves 3 parallel treatment arms: PRCL-02 Dose 1, PRCL-02 Dose 2, and placebo. All patients will receive study drug, to be administered orally once daily, for 12 weeks. The planned active doses are:

Dose 1: Loading dose of 150 mg followed by a once daily maintenance dose of 25 mg, commencing on Day 2 and continuing for 12 weeks.

Dose 2: Loading dose of 300 mg followed by a once daily maintenance dose of 50 mg, commencing on Day 2 and continuing for 12 weeks.

Doses may be revised upwards or downwards based on new safety information and exposure data becoming available during the course of the study.

2.5. Definition of Baseline Assessments

Day 1 is defined in the protocol as the first day of Visit 2. The last assessment made on or before this date will be defined as the Baseline assessment. Adverse events that occurred on Day 1 will be assumed to be treatment-emergent, unless there is evidence to the contrary.

2.6. Definition of Study Visit

Patient data will be analyzed according to the nominal visit collected in the eCRF. Unscheduled visits at which safety data is collected (e.g. labs and ECGs) may result in clinically significant findings or withdrawal, which will be included in adverse event and/or disposition summaries.

